**DOCUMENT HISTORY**

Document	Date of Issue	Summary of Change
Revised Protocol 06	15-Aug-2018	Incorporates Administrative Letter 03 and clarifies that treatment algorithm in Appendix 10 applies to both infusion reactions and cytokine release syndrome. The revisions also includes title change to Appendix 5 to clarify that the algorithms are applicable to both nivolumab and BMS-986277-mediated IMAE.
Administrative Letter 03	04-Jun-2018	To add the IND number on the title page of the protocol.
Revised Protocol 05	18-May-2018	
To add an additional expansion cohort and long-term follow-up requirements as well as limit BMS-986277 dosing to 2 cycles:
 
 
• Schedule of Activities tables were updated
 
• Clinical experience with enadenotucirev was updated
 
• [REDACTED]
 
• Overall design was updated
 
• Blinded independent central review of efficacy scans was clarified
 
• [REDACTED]
 
• [REDACTED]
 
• [REDACTED]
 
• Inclusion and exclusion criteria were updated
 
• Lifestyle restrictions were added
 
• Treatments administered were updated
 
• Dose-limiting toxicities were updated
 
• Treatment delays were updated
 
• Prohibited and/or restricted treatments were updated
 
• Efficacy assessments were updated
 
• Imaging assessments were updated
 
• Adverse event and serious adverse event information was updated
 
• Pregnancy was updated
 
• Clinical safety laboratory assessments were updated
 
• Pharmacokinetic section and tables were updated
 
• Additional research collection was updated
 
• [REDACTED]
 
• Statistical considerations was updated
 
• Appendices 1, 2, 3, 4, and 8 were updated
 
• Appendix 11 was added
 
 
Typographical errors were corrected, and edits were made for consistency and clarity.

Revised Protocol 04	02-Mar-2018	To implement revisions requested by a health authority [REDACTED]

Document	Date of Issue	Summary of Change
Revised Protocol 03	15-Dec-2017	
Incorporates Administrative Letters 01 and 02 and the following:
 
 
• Schedule of Activities tables were updated
 
• Benefit/risk was updated
 
• Exploratory objectives were updated
 
• Overall design was updated
 
• Inclusion and exclusion criteria were updated
 
• Required concomitant medications were updated
 
• Clinical safety laboratory assessments were updated
 
• Pharmacokinetics tables were updated
 
• [REDACTED]
 
• Additional research collection was updated
 
• Immunogenicity analyses was updated
 
• Appendix 5 title was updated
 
• Appendix 9 was updated
 
• Appendix 10 was added
 
• Typographical errors were corrected, and edits were made for consistency and clarity.
 

Administrative Letter 02	11-Dec-2017	To add a up to + 7 day dosing window to Day 15 in Cycle 1 and clarify the dosing window in order to alleviate administrative complications at clinical sites.
Administrative Letter 01	07-Nov-2017	To correct that only the participant number and the dose will be recorded on the syringe as well as to clarify how information will be collected.
Revised Protocol 02	24-Oct-2017	To prevent misinterpretation of the pre-medication recommendations for nivolumab treatment and to clarify infusion duration by dose.
Revised Protocol 01	27-Sep-2017	Updated the potency of BMS-986277 drug to be supplied.
Original Protocol	08-Sep-2017	Not applicable

## 1 SYNOPSIS

**Protocol Title:** Phase 1/2a First in Human Study of BMS-986277 Administered Alone and in Combination with Nivolumab in Advanced Epithelial Tumors

**Short Title:**

An Investigational Immuno-Therapy Study of BMS-986277 Alone and in Combination with Nivolumab in Epithelial Cancers

**Study Phase:** Phase 1/2a

**Research Hypothesis:**

The CD80/ $\alpha$ CD3 Oncolytic Virus (BMS-986277) is safe to be administered systemically to participants with advanced epithelial tumors alone and in combination with the anti-PD-1 checkpoint inhibitor, nivolumab. BMS-986277 will increase immune activation in the tumor microenvironment (TME) of advanced or metastatic epithelial tumors making tumors more susceptible to nivolumab-mediated anti-tumor activity.

[figure not shown]
**Study Population:**

Male and females, 18 years of age and older, diagnosed with metastatic or advanced colorectal cancer (CRC), prostate cancer, pancreatic cancer, triple-negative breast cancer (TNBC), ovarian cancer, or urothelial carcinoma, with tumor accessible for biopsy.

**Objectives and Endpoints:**

Objectives	Endpoints
Primary	

To characterize the safety and tolerability of BMS-986277 administered alone and in combination with PD-1 inhibitor, nivolumab, in advanced epithelial tumors

To determine the RD and RP2D and dosing schedule of BMS-986277 administered alone (RD) and in combination with nivolumab in participants with advanced epithelial tumors

	

Incidence of AEs, SAEs, AEs meeting protocol-defined DLT criteria, AEs leading to discontinuation, and AEs resulting in death

Incidence of clinical laboratory test abnormalities

Vital sign abnormalities or other safety biomarkers

Objectives	Endpoints
Secondary	

 
To explore the preliminary anti-tumor activity of BMS-986277 alone and in combination with nivolumab in participants with advanced epithelial tumors (RECIST v1.1 and PCWG3)
 
	
 
ORR, DCR, mDOR, mPFS, and PFSR at 8, 16, and 24 weeks depending on indication
 

 
To assess the PK and IMG of BMS-986277 in blood following monotherapy or combination treatment
 
	
 
Summary measures of PK and IMG parameters of BMS-986277
 

AE = adverse events; BICR = blinded independent central review; DCR = disease control rate; DLT = dose-limiting toxicity; IMG = immunogenicity; iRECIST = immune Response Evaluation Criteria in Solid Tumors; mDOR = median duration of response; mOS = median overall survival; mPFS = median progression-free survival; NPV = negative predictive value; ORR = objective response rate; OS = overall survival; OSR = overall survival rate; PCWG3 = Prostate Cancer Clinical Trials Working Group 3; PK = pharmacokinetics; PFSR = progression-free survival rate; PPV = positive predictive value; RD = recommended dose; RECIST = Response Evaluation Criteria in Solid Tumors; RP2D = recommended Phase 2 dose; SAE = serious adverse events; TPR = true positive rate

**Overall Design:**

[figure not shown]
This is a Phase 1/2a, multicenter, open-label, non-randomized study of CD80/ $\alpha$ CD3 Oncolytic Virus (BMS-986277) alone or in combination with nivolumab for the treatment of metastatic or advanced epithelial tumors in male and female participants.

The study will be conducted in 3 Parts:

- Part 1: a single agent monotherapy dose escalation to establish the Bayesian Logistic Regression Model-recommended dose (BLRM-RD) of BMS-986277 based on safety and tolerability
- Part 2: a combination dose escalation to establish the BLRM-RD of BMS-986277 (using the RD from Part 1) in combination with nivolumab (480 mg every 4 weeks [Q4W])
- Part 3: a 3-cohort expansion
  - Cohort 1 will treat participants with low CD8 tumor-infiltrating lymphocytes (TILs) (< 2%) with BMS-986277 (using the RD from Part 2) in combination with nivolumab (480 mg Q4W)
  - Cohort 2 will treat participants with mid CD8 TILs ( $2\% \leq \text{CD8} < 20\%$ ) with BMS-986277 (using the RD from Part 2) in combination with nivolumab (480 mg Q4W)
  - Cohort 3 will treat participants with high CD8 TILs ( $\geq 20\%$ ) with BMS-986277 monotherapy (using the RD from Part 1) to further characterize the pharmacodynamics of BMS-986277 monotherapy. Following BMS-986277 monotherapy treatment (up to 2 cycles), participants will have the option to receive nivolumab treatment (480 mg Q4W) to explore sequential dosing.

The study design schematic is presented in [Figure 1](#).

**Figure 1:** Study Design Schematic

**For Parts 1 and 2, dosing of initial participants will be staggered by 7 days to mitigate against unexpected adverse drug reaction (ADR) as follows:**

- Lowest Dose level: the first 3 participants may not begin dosing within 7 days of each other
  - Other dose levels: the first 2 participants may not begin dosing within 7 days of one another
- a Additional participants (up to a total of 12) may be treated at any dose level to further evaluate the safety, PK, and/or pharmacodynamic profile.
- b As a minimum of 3 participants with low (< 2%) or mid (2% ≤ CD8 < 20%) CD8 TIL are required to be evaluated at each dose level, CD8 biomarker testing of fresh tumor samples (Section 9.8) will be required at study entry.
- c Following 2 cycles of BMS-986277 monotherapy, participants may receive optional nivolumab treatment (480 mg Q4W) for up to 26 cycles if eligibility criteria continue to be met (see Sections 6.1 and 6.2). Participants whose disease progresses prior to receiving Cycle 2 of BMS-986277 may also receive nivolumab treatment if eligibility criteria continue to be met, skipping any remaining monotherapy visits and proceeding directly to Cycle 3, optional nivolumab treatment. For participants whose disease is responding (complete or partial) per RECIST v1.1 or PCWG3 at the 8 week scan, treatment must be discussed and agreed upon with the Medical Monitor (or designee) prior to the start of the optional subsequent nivolumab treatment.
- BLRM-RD = Bayesian Logistic Regression Model-Recommended Dose; D = day; IV = intravenous; N = number; Q4W = every 4 weeks; RD = recommended dose; TIL = tumor-infiltrating lymphocytes; VP = viral particles.

### Number of Participants:

- Part 1 (Monotherapy Dose Escalation - BMS-986277)
  - Initially, 3-6 participants per BMS-986277 monotherapy dose level, for a total of up to 24 participants. Additional participants (up to a total of 12) may be treated at any dose level to further evaluate the safety, PK, or pharmacodynamic profile. Therefore, the total sample size is up to 72.
- Part 2 (Combination Dose Escalation - BMS-986277 and nivolumab)
  - Initially, 3-6 participants per combination dose level. Additional participants (up to a total of 12) may be treated at any dose combination below or at the BLRM-RD for further evaluation of the safety, PK, or pharmacodynamic profile. Therefore, the total sample size is up to 36.
- Part 3 (Combination Expansion)
  - Cohorts 1-2 (BMS-986277 and nivolumab): Up to 40 evaluable participants per cohort. See [Section 10.1](#) for further details on sample size calculation.
  - Cohort 3 (BMS-986277 monotherapy with option for subsequent nivolumab therapy): Up to approximately 12 participants evaluable for pharmacodynamic endpoints will be treated in this cohort. See [Section 10.1](#) for further details on sample size.

### Treatment Arms and Duration:

- Part 1: a monotherapy dose escalation of BMS-986277.
  - Four dose levels:  $3 \times 10^{10}$  viral particles (vp),  $3 \times 10^{11}$  vp,  $1 \times 10^{12}$  vp, and  $3 \times 10^{12}$  vp.
  - 6-week DLT evaluation period to assess safety with multiple injections which may be extended due to dose delays.
  - Dosing for the initial participants into each cohort in Part 1 will be staggered by 7 days to monitor for sentinel events.
  - Participants will receive 2 cycles (Cycle 1: 42 days, Cycle 2: 28 days) of BMS-986277.
- Part 2: a combination dose escalation of BMS-986277 (using the RD from Part 1; up to 2 cycles) in combination with nivolumab (480 mg Q4W; up to 26 cycles).
  - Participants will receive BMS-986277 at the BLRM-RD, or a lower dose than the BLRM-RD from Part 1.
    - ◆ Dosing for the initial participants into each cohort will be staggered by 7 days to monitor for sentinel events.
- Part 3: a 3-cohort expansion.
  - In Cohort 1, participants with low CD8 TILs ( $CD8 < 2\%$ ) will be treated with BMS-986277 (using the RD from Part 2; up to 2 cycles) in combination with nivolumab (480 mg Q4W; up to 26 cycles).
  - In Cohort 2, participants with mid CD8 TILs ( $2\% \leq CD8 < 20\%$ ) will be treated with BMS-986277 (using the RD from Part 2; up to 2 cycles) in combination with nivolumab (480 mg Q4W; up to 26 cycles).
  - In Cohort 3, participants with high CD8 TILs ( $\geq 20\%$ ) will be treated with BMS-986277 monotherapy (using the RD from Part 1; up to 2 cycles) with an option for subsequent nivolumab treatment (480 mg Q4W; up to 26 cycles).

**Study treatment:**

Study Drug for CA034001					
Medication	Potency	IP a /Non-IP	Blinded or Open Label	Packaging / Appearance	Storage Conditions (per label)
BMS-986277 Solution for Injection	2 × 10  vp/mL 0.5 mL vial	IP a	Open Label	Vial	Refer to the label on container and/or pharmacy manual
Nivolumab BMS-936558-01 Solution for Injection	100 mg (10 mg/mL) 40 mg (10 mg/mL)	IP a	Open label	Vial	Refer to the label on container and/or pharmacy manual

Abbreviations: IP = investigational product

a IP is also known as IMP in some regions.

**Data Monitoring Committee: No**

Bristol-Myers Squibb (BMS) has developed a multi-layered process to ensure safety monitoring through close collaboration of study site investigators, the BMS study team, and the BMS Global Pharmacovigilance and Epidemiology (GPVE) led Medical Surveillance Team (MST). This collaborative process constitutes the safety monitoring plan for the study. To support safety oversight, BMS has established ongoing processes for collection, review, analysis, and submission of individual adverse event reports and their aggregate analyses. Because this is an open-label study, GPVE, the BMS medical monitor (or designee), and the investigators will have access to all data necessary for safety evaluation.

BMS GPVE is an internal group that operates independently from the clinical team to monitor safety across all BMS protocols, and analyze all data in an unblinded fashion. Within BMS, an MST is established for investigational therapies under clinical development, and a member of GPVE chairs this team. In addition, signal detection is performed at least monthly and ad hoc throughout the study by the MST composed, at a minimum, of the GPVE medical safety assessment physician (Chairman of the MST) and GPVE single case review physician, the study Medical Monitor (or designee), the study biostatistician, and epidemiologist; all of whom, analyze the data in an unblinded fashion. Furthermore, the MST routinely monitors for actual or potential issues related to participant safety that could result in a change in the medical risk-benefit balance associated with the use of study treatment(s).

## 2 SCHEDULE OF ACTIVITIES

**Table 2-1: Screening Procedural Outline (All Parts)(CA034001)**

Procedure a	Screening Visit	Notes
Eligibility Assessments		
Informed Consent	X	A participant is considered enrolled only when a protocol specific informed consent is signed.
Inclusion/Exclusion Criteria	X	All inclusion/exclusion criteria should be assessed and confirmed prior to first dose. See Sections 6.1 and 6.2 .
Medical History	X	Include any toxicities or allergy related to previous treatments.
Prior Anti-cancer Therapy	X	
Prior Radiotherapy	X	
ECOG	X	Within 14 days prior to first dose. See Appendix 6 .
Tumor Tissue Sample	X	Participants must provide a fresh tumor biopsy within 35 days prior to first dose from the disease site (when possible) or from any metastatic site when the primary site is not available. For Parts 2 and 3 of the study, part of the samples will be used prospectively for CD8 evaluation by IHC. All tissue samples received must be suitable for testing to verify PD-L1 and CD8 status. See Section 9.8 and the Laboratory Manual for further details on procedures for collecting fresh tumor samples.
CD8 T-cell Assay	X	For Part 1, retrospective evaluation and not influencing enrollment. For Part 2, prospective evaluation to determine a minimum number of participants with low or mid CD8 TILs per dose level. For Part 3, prospective evaluation to determine cohort assignment. See Sections 5.1.2 and 5.1.3 .
Safety Assessments		
Assessment of Signs and Symptoms	X	Within 14 days prior to first dose.
PE	X	If the screening PE is performed within 24 hours prior to dosing on Day 1, then a single exam may count as both the screening and predose evaluation.
Physical Measurements	X	Includes height and weight.

**Table 2-1: Screening Procedural Outline (All Parts)(CA034001)**

Procedure a	Screening Visit	Notes
Vital Signs	X	Includes body temperature, respiratory rate, seated BP and heart rate. BP and heart rate should be measured after the participant has been resting quietly for at least 5 minutes. Consider alternate position(s) for vital sign collection.
Pulse Oximetry	X	Oxygen saturation at rest.
Concomitant Medication Use	X	Includes medications taken within 14 days prior to first dose.
12-lead ECG	X	Within 14 days prior to first dose. ECGs should be recorded after the participant has been supine for at least 5 minutes.
Chemistry	X	To be performed locally within 14 days prior to first dose. See Section 9.4.5 .
Hematology	X	To be performed locally within 14 days prior to first dose. See Section 9.4.5 .
Thyroid Function Tests	X	To be performed locally within 14 days prior to first dose. See Section 9.4.5 .
Urinalysis	X	To be performed locally within 14 days prior to first dose. See Section 9.4.5 .
Serology Tests	X	To be performed locally within 28 days prior to first dose. See Section 9.4.5 .
Pregnancy Test	X	For WOCBP only. Serum or urine pregnancy test (minimum sensitivity 25 IU/L or equivalent units of HCG) to be done at screening visit and within 24 hours prior to first dose. See Section 9.4.5 .
FSH	X	Only required to confirm menopause in women with age < 55. See Section 9.4.5 and Appendix 4 .
AE Reporting		
Monitor for SAE	X	All SAEs must be collected from the date of participant's written consent until 60 days (participants treated with BMS-986277 monotherapy) or 100 days (participants treated with BMS-986277 and nivolumab) post discontinuation of dosing. See Section 9.2.1 and Appendix 3 .
Efficacy Assessments		
Body Imaging	X	Contrast enhanced CT of the chest, abdomen, pelvis, and all other known and/or suspected sites of disease should occur within 28 days prior to first dose. See Section 9.1.1 for further details. For participants with TNBC without measurable lesions outside the breast, contrast enhanced MRI of the breasts should also be performed.

**Table 2-1: Screening Procedural Outline (All Parts)(CA034001)**

Procedure a	Screening Visit	Notes
Brain Imaging	X	MRI of the brain without and with contrast is required for participants with known (if not had brain imaging within 30 days of study drug administration) or suspected brain metastases. CT of the brain without and with contrast can be performed if MRI is contraindicated. See Section 9.1.1 for further details.
Bone Scan	X	Required for participants with prostate cancer only (PCWG3 Assessment). Others only as clinically indicated (eg, participants with history or symptoms of bone metastases). See Section 9.1.1 for further details.
IRT		
Register Participant in IRT	X	IRT contact must occur for participant number assignment at the time informed consent is obtained.

Abbreviations: AE = adverse event; BP = blood pressure; CT = computed tomography; ECG = electrocardiogram; ECOG = Eastern Cooperative Oncology Group; FSH = follicle stimulating hormone; HCG = human chorionic gonadotropin; IHC = immunohistochemistry; IRT = interactive response technology; MRI = magnetic resonance imaging; PCWG3 = Prostate Cancer Clinical Trials Working Group 3; PD-L1 = programmed death-ligand 1; PE = physical examination; SAE = serious adverse events; TIL = tumor-infiltrating lymphocyte; TNBC = triple-negative breast cancer; WOCBP = women of childbearing potential

a Some of the assessments referred to in this section may not be captured as data in the electronic case report form (eCRF). They are intended to be used as safety monitoring by the treating physician. Additional testing or assessments may be performed as clinically necessary or where required by institutional or local regulations.

**Table 2-2: On-Treatment Assessment Schedule (Monotherapy Dose Escalation - BMS-986277 [Part 1])(CA034001)**

Procedure a	Cycle 1 (42 days: 14 day lead-in period + 28 days) b				Cycle 2 (28 days) b				EOT c	Notes
	D1	D8 ( $\pm$ 3 days)	D15 d,e , D17 e , D19 e	D29 and D36 ( $\pm$ 3 days)	D1 ( $\pm$ 3 days)	D3 e and D5 e	D8 ( $\pm$ 3 days)	D15 and D22 ( $\pm$ 3 days)		
Safety	■	■	■	■	■	■	■	■	■	
Targeted PE, Physical Measurements (weight only), Vital Signs, ECOG Performance Status	X	X	X	X	X	X	X	X	X	On each BMS-986277 dosing day, assessments (vital signs) will be performed at predose and every 15 minutes ( $\pm$ 5 minutes) until 60 minutes following completion of infusion and then at 4 hours ( $\pm$ 30 minutes) and 8 hours ( $\pm$ 1 hour) postdose.
Pulse Oximetry	X	X	X	X	X	X	X	X	X	On each BMS-986277 dosing day, oxygen saturation at rest will be performed at predose and every 15 minutes ( $\pm$ 5 minutes) until 60 minutes following completion of infusion and then at 4 hours ( $\pm$ 30 minutes) and 8 hours ( $\pm$ 1 hour) postdose.

**Table 2-2: On-Treatment Assessment Schedule (Monotherapy Dose Escalation - BMS-986277 [Part 1])(CA034001)**

Procedure a	Cycle 1 (42 days: 14 day lead-in period + 28 days) b				Cycle 2 (28 days) b				EOT c	Notes
	D1	D8 (± 3 days)	D15 d,e , D17 e , D19 e	D29 and D36 (± 3 days)	D1 (± 3 days)	D3 e and D5 e	D8 (± 3 days)	D15 and D22 (± 3 days)		
SAE Assessment	Continuously									
AE Assessment	Continuously									
Laboratory Tests	On-study laboratory tests to be done on-site/local within 72 hours prior to dosing. For the first dosing visit, labs need not be repeated if they were performed within 72 hours and the results are available and have been reviewed for eligibility. See Section 9.4.5 .									
Chemistry	X	X	X	X	X	X	X	X	X	X
Hematology	X	X	X	X	X	X	X	X	X	X

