### **7.4 Dosage Modification**

#### **7.4.1 Dose-Limiting Toxicities**

For the purpose of guiding dose escalation, DLTs will be defined based on the incidence, intensity, and duration of AEs for which no clear alternative cause is identified. The DLT evaluation period will be 42 days (6 weeks). In the event of dose delays for reasons other than a potential DLT, the DLT evaluation period may be extended to include at least 28 days after the start of the sequential doses in Part 1 or at least 14 days after the start of Cycle 2 Day 1 sequential doses in Part 2. Participants requiring dose delays >7 days may be replaced for the purposes of DLT evaluation

but permitted to remain on study treatment unless permanent discontinuation criteria (Section 8.1) are met.

In all study parts, participants who complete the first cycle and do not have a DLT, have not had clinical evidence of disease progression, and are considered suitable for further treatment may receive up to 1 additional cycle of BMS-986277.

Additionally DLT's as defined below will require permanent discontinuation for all study participants regardless of treatment cycle.

In Parts 1 and 2, participants who discontinue due to a DLT during the DLT evaluation period, will be considered as DLT-evaluable participants. Participants who withdraw from the study during the DLT evaluation period for reasons other than a DLT may be replaced with a new participant at the same dose level. The incidence of DLT(s) during the DLT evaluation period will be used in dose escalation decisions and to define the BLRM-RD. AEs occurring after the DLT period will be considered for the purposes of defining the BLRM-RD upon agreement between the Sponsor, Medical Monitor (or designee), and investigators.

Participants experiencing a DLT will enter the safety follow-up period of the study. DLTs occurring after the 6-week DLT evaluation period for Part 1 will be accounted for in determining the BLRM-RD for the combination part.

A DLT is defined as one of the following and considered by the Investigator to be possibly, probably or definitely related to BMS-986277 and/or nivolumab.

AEs will be graded according to the NCI CTCAE v4.03, as listed below:

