### 1) Hepatic Non-hematological DLT

Any one of the following study treatment-related events will be considered a hepatic DLT:

- Any Grade  $\geq 3$  elevation of aspartate aminotransferase (AST), alanine aminotransferase (ALT), or total bilirubin.
- Grade 2 AST or ALT with symptomatic liver inflammation (eg, right upper quadrant tenderness, jaundice, pruritus).
- AST or ALT  $> 3 \times$  ULN and concurrent total bilirubin  $> 2 \times$  ULN without initial findings of cholestasis (elevated serum alkaline phosphatase [ALP] [eg, findings consistent with Hy's law or FDA definition of potential drug-induced liver injury or potential drug-induced liver injury [p-DILI]). Note that this special category of DLT uses ULN rather than Common Toxicity Criteria (CTC) grade for definition.

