### 4) Hematologic DLT

- Grade 4 neutropenia  $\geq$  5 days in duration
- Grade 4 thrombocytopenia or Grade 3 thrombocytopenia with clinically significant bleeding or any requirement for platelet transfusion
- Grade 4 anemia not explained by underlying disease
- Grade 4 febrile neutropenia
- Grade 3 febrile neutropenia that lasts  $>$  48 hours
- Grade  $\geq$  3 hemolysis (ie, requiring transfusion or medical intervention such as steroids)

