## 9 STUDY ASSESSMENTS AND PROCEDURES

- Study procedures and timing are summarized in the Schedule of Activities (see [Section 2](#)).
- Protocol waivers or exemptions are not allowed.
- All immediate safety concerns must be discussed with the Sponsor immediately upon occurrence or awareness to determine if the participant should continue or discontinue treatment.
- Adherence to the study design requirements, including those specified in the Schedule of Activities, is essential and required for study conduct.
- All screening evaluations must be completed and reviewed to confirm that potential participants meet all eligibility criteria before treatment assignment. The investigator will maintain a screening log to record details of all participants screened and to confirm eligibility or record reasons for screening failure, as applicable.
- Procedures conducted as part of the participant's routine clinical management (eg, blood count) and obtained before signing of informed consent may be utilized for screening or baseline purposes provided the procedure meets the protocol-defined criteria and has been performed within the timeframe defined in the Schedule of Activities (see [Section 2](#)).
- Safety assessments should continue as specified in the Schedule of Activities in case of dose delay.

Additional measures, including non-study required laboratory tests, should be performed as clinically indicated or to comply with local regulations. Laboratory toxicities (eg, suspected drug induced liver enzyme evaluations) will be monitored during the follow-up phase via on site/local laboratories until all study drug related toxicities resolve, return to baseline, or are deemed irreversible.

If a participant shows pulmonary-related signs (hypoxia, fever) or symptoms (eg, dyspnea, cough, fever) consistent with possible pulmonary AEs, the participant should be immediately evaluated to rule out pulmonary toxicity, according to the suspected pulmonary toxicity management algorithm in the nivolumab IB.

Some of the assessments referred to in this section may not be captured as data in the eCRF. They are intended to be used as safety monitoring by the treating physician. Additional testing or

assessments may be performed as clinically necessary or where required by institutional or local regulations.

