    - ◆ Additionally, a weekly dosing schedule was investigated at doses of  $3 \times 10^{12}$  and  $6 \times 10^{12}$  where treatment was administered on Days 1, 3, 5, 8, and 15 in the first cycle and on Days 1, 8, and 15 in subsequent cycles.
  - In ColoAd1-1002: a single cycle of enadenotucirev at a dose of  $1 \times 10^{12}$  vp was given on Days 1, 3, and 5.
  - Across ColoAd1-1001 and ColoAd1-1002, 40 subjects received 1 cycle of enadenotucirev and 33 subjects received >1 cycle
  - Two subjects experienced similar DLTs after the first dose of enadenotucirev at  $1 \times 10^{13}$  vp. One subject experienced hypoxia and dyspnoea and the second subject experienced acute

lung injury. These events were all considered Grade 3 per the NCI CTCAE, definitely related to treatment, and resulted in discontinuation of treatment.

- The data are summarized in Table 1.

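### Optional improvement: with on-schedule dosing, Part 1 Cycle 1 has no chemistry or hematology between the predose Day 19 sample and Day 29 ± 3; the existing 48-hour blood draw could carry them

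*Protocol*

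**What the plan says.** Protocol Table 2-2 (Part 1) marks chemistry and hematology in Cycle 1 on Days 1, 8, 15, 17 and 19. The next column is headed "D29 and D36 (± 3 days". Dosing-day samples precede the infusion: "On-study laboratory tests to be done on-site/local within 72 hours prior to dosing". The Day 19 sample therefore cannot show any effect of the Day 19 infusion.

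Seven other three-infusion sequences exist: Part 1 Cycle 2, and Cycles 1 and 2 of Part 2, of Part 3 Cohorts 1-2 and of Part 3 Cohort 3. Each is dosed on Days 1, 3 and 5 and has chemistry and hematology at Day 8 ± 3 (Tables 2-2 to 2-5).

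Section 7.4.1 sets the window: "The DLT evaluation period will be 42 days (6 weeks". Cycle 2 of Part 1 starts no sooner than 42 days after C1D1, so Days 15, 17 and 19 are the only three-infusion sequence in that window. Two kinds of laboratory DLT need no minimum duration: Grade 3 or higher "elevation of aspartate aminotransferase (AST), alanine aminotransferase (ALT), or total bilirubin", and "Grade 4 thrombocytopenia or Grade 3 thrombocytopenia with clinically significant bleeding".

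Table 9.5-1 schedules a blood draw at C1D21, 48 hours after the third infusion, for PK and ADA only. Section 9.5 says on-treatment PK samples follow the actual dosing day.

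**The concern.** Part 1 Cycle 1 is the first repeat-dose exposure in a first-in-human trial, and its DLTs feed the dose-escalation model. Yet on nominal days it has the longest wait for a laboratory test after the third infusion of all eight sequences. A transaminase rise or platelet fall without symptoms could begin soon after Day 19 and resolve before Day 29. It would meet the DLT definition, but no scheduled sample would show it. The unredacted text gives no reason for the wider spacing.

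**Working it through.** **Day counts.** Part 1 Cycle 1: 29 − 19 = 10 days, or 240 h; with ± 3 days, 7 to 13. The other seven: 8 − 5 = 3 days, or 72 h; with ± 3 days, 0 to 6. Table 9.5-1 shows the same intervals, labelling C1D29 as 240:00 and C2D8 as 72:00.

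**Reading of the table.** In the available text the chemistry and hematology rows of Table 2-2 carry ten marks for nine visit columns. No page of the table has a header for a further visit, and the urinalysis row has nine marks. The tenth is read as lying in the Notes column.

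**Longest laboratory-free stretch after the third infusion.** Take visits as uniform in their windows and the third infusion as time 0.
- Now: the next sample is U(7, 13). P(over 10 days) = 3/6 = 50%; maximum 13.
- Elsewhere: Day 8 is U(0, 6) and Day 15 is U(7, 13). A stretch over 10 days needs Day 15 − Day 8 > 10, with probability 4.5/36 = 12.5%. The maximum is again 13 (Day 8 visit at 0, Day 15 visit at 13).
- With tests at C1D21 (time 2): maximum 13 − 2 = 11.

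**Chance that a scheduled sample falls within an event.** The documents give no onset times or durations for laboratory events, so both are assumptions. Take a 5-day event with onset o uniform on 1 to 4 days.
- Now: Day 29 catches it only if o > 2, with probability (o − 2)/6. Averaged over onset, (1/3) × ∫ from 2 to 4 of (o − 2)/6 = 2/18 = 11.1%.
- With C1D21: every event with o ≤ 2 is also caught, which is 1/3 of them. 33.3% + 11.1% = 44.4%.

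Simulation with 2,000,000 draws per case agrees and gives the wider range, with dosing on schedule:

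| Onset (days) | Duration (days) | Now | Day 8 ± 3 pattern | With C1D21 tests |
|---|---|---|---|---|
| 1-4 | 3 | 0% | 47% | 33% |
| 1-4 | 5 | 11% | 64% | 44% |
| 1-4 | 7 | 42% | 78% | 67% |
| 1-4 | 10 | 89% | 97% | 97% |
| 0-10 | 5 | 43% | 69% | 63% |
| 0-10 | 10 | 91% | 98% | 98% |
| 4-10 | 5 | 66% | 69% | 66% |
| 4-10 | 10 | 98% | 98% | 98% |

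For 14-day events the three schedules do not differ.

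**Late dosing, visits on nominal days, 5-day events, onset 1-4.**
- Third infusion 3 days late: Day 29 becomes U(4, 10). Now: mean of (o + 1)/6 = 3.5/6 = 58.3%. With C1D21: 1/3 + 2/3 × 4/6 = 77.8%.
- Third infusion 7 days late (Day 26): Day 29 ± 3 falls 0 to 6 days after it, which is the pattern used elsewhere. Now 64.5%; with C1D21 about 73%.

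**The case against.** The strongest reply is that no decision is taken inside the gap. After Day 19 there is no virus dose until Cycle 2, and the Day 29 and Day 36 tests come first. Next-cohort recommendations use DLT-period data, so those results are available then too. This stands. A reader might infer that participants are re-dosed unmonitored; the schedule does not support that.

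The gap also depends on punctual dosing. Day 15 may be given up to 7 days late, and at that limit the asymmetry is gone. The permitted maximum interval is 13 days in every sequence, so it would be wrong to infer that Part 1 Cycle 1 alone allows a longer one. Both points stand.

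Other cover exists. AEs are assessed continuously, and extra measures, "including non-study required laboratory tests, should be performed as clinically indicated". Cycle 2 has Day 8 tests at the same dose, and "DLTs occurring after the 6-week DLT evaluation period for Part 1 will be accounted for in determining the BLRM-RD for the combination part". These reduce the effect, but they do not reliably reveal a silent event that has already resolved.

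The known parent-virus DLTs also point away from silent laboratory events: "Two subjects experienced similar DLTs after the first dose of enadenotucirev", and these were respiratory. That limits how likely the scenario is. It does not exclude it, because Appendix 9 (Section 1.2) allows for higher toxicity of BMS-986277 through T-cell activation.

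Finally, the absence of C1D21 from Table 2-2 is not a defect, since that table refers to Table 9.5-1 for PK sampling. This is correct.

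**Conclusion.** The asymmetry is real on nominal days, and closing part of it is a cheap optional improvement. The size depends on assumed timing. For 5-day events, tests at C1D21 add about 33 points if onset is at 1 to 4 days (11% to 44%), 20 points if onset is at 0 to 10 days (43% to 63%), and nothing if onset is at 4 days or later. With onset at 1 to 4 days, the gain falls to about 20 points if the third infusion is 3 days late (58% to 78%) and about 9 if it is 7 days late (64% to 73%). For 10-day events with on-schedule dosing it is 8 points or less. The day-2 sample helps only for events already present at 48 hours.

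A reader might infer that the observed DLT rate is biased downward, or that the recommended dose would change. The documents do not support either: they give no frequency, onset or duration for silent laboratory events, and most of the gain needs an event that is both early and short.

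**What to change.** Add local chemistry and hematology to the existing C1D21 (48-hour) blood draw in Table 9.5-1. Show it in Table 2-2 as a safety laboratory time point, timed to the actual third infusion so that it moves with late dosing. The cost is one extra local sample per Part 1 participant and a schedule-table amendment; no new visit is needed.

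A Day 22 ± 3 visit would copy the pattern used elsewhere and catch more short events when dosing is on schedule. It is not recommended: it needs a new visit, and if the third infusion slips to Day 26 its whole window (Days 19 to 25) falls before that infusion. In that case it adds nothing (64.5% with or without it for 5-day events, onset 1 to 4 days).
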